10.3.1 Data Audit

After all subject data have been submitted and data queries addressed, the database will be considered ready to lock.

10.4 ADVERSE EXPERIENCE REPORTING

See **Table 5** above for the flow chart reflecting AE and SAE reporting.

11 HUMAN SUBJECTS

11.1 INSTITUTIONAL REVIEW BOARD REVIEW AND INFORMED CONSENT

This protocol, the informed consent document, and any subsequent modifications will be reviewed and approved by the IRBs responsible for oversight of the study at each study site. Any substantial changes in protocol must be approved by the DSMB. The consent form will describe the purpose of the study, the procedures to be followed, Certificate of Confidentiality language, and the risks and benefits of participation. A list of key elements to be included in the consent will be prepared by the CCC, reviewed by the DCC, and reviewed and ultimately approved by the DSMB. The approved consent at UCSF will be used as a template for preparation of the consent at the sites. A copy of the signed consent form will be given to the parent or legal guardian, a copy placed in the patient's chart, and the original signed consent will be stored by the site coordinator.

11.2 SUBJECT CONFIDENTIALITY

All laboratory specimens, evaluation forms, reports, and other records that leave the site will be identified only by the Study Identification Number (Subject Study ID), as well as date and time for laboratory specimens, to maintain subject confidentiality. All records will be kept in a locked file cabinet. All computer entry and networking programs will be performed using Subject Study ID only. Clinical information will not be released without written permission of the subject, except as necessary for monitoring by the IRB, the FDA, the NINDS, and by the CCC and DCC.

11.3 STUDY MODIFICATION/DISCONTINUATION

The study may be modified or discontinued at any time by a local IRB, the NINDS, the DSMB, or the FDA as part of their duties to ensure that research subjects are protected. Any changes to the protocol require a written protocol amendment that must be approved by the Executive and Steering Committees and by the DSMB prior to implementation. Amendments that affect patient eligibility, study protocol, or consent changes require additional approval by the IRB at each site. These amendments, should they be required, will become a part of the protocol and maintained by the Investigator as part of the study documentation. For amendments affecting only administrative aspects of the study that do not require formal IRB approval, the IRB at each of the sites must be informed of such changes. Other

changes in the study conduct are not permitted. Any unforeseen changes must be recorded in the clinical study report.

12 PUBLICATION OF RESEARCH FINDINGS

Publication of the results of this trial will be governed by the policies and procedures developed by the Executive Committee. Any presentation, abstract, or manuscript will be made available for review by the NINDS prior to submission.

14.1 ACRONYMS

AE	Adverse Event
aEEG	Amplitude-integrated EEG
AIMS	Alberta Infant Motor Scale
ANCOVA	Analysis of Covariance
AUC	Area Under the Curve
Bayley III	Bayley Scales of Infant and Toddler Development, 3 rd Edition
BDNF	Brain-Derived Neurotrophic Factor
BEAM	Beneficial Effects of Antenatal Magnesium Sulfate
BGT	Basal Ganglia and Thalamus
CBCL	Child Behavior Checklist
CCC	Clinical Coordinating Center
cEEG	Continuous EEG
CNS	Central Nervous System
CONSORT	Consolidated Standards of Reporting Trials
CP	Cerebral Palsy
CPAP	Continuous Positive Airway Pressure
CRF	Case Report Form
CSF	Cerebrospinal Fluid
DCC	Data Coordinating Center
DIC	Disseminated Intravascular Coagulation
DSMB	Data Safety Monitoring Board
DSMP	Data Safety Monitoring Plan
DTI	Diffusion Tensor Imaging
ECMO	Extracorporeal Membrane Oxygenation
EEG	Electroencephalogram
ELGAN	Extremely Low Gestational Age Newborns
Epo	Erythropoietin
Epo-R	Erythropoietin Receptor
ERK1	Extracellular Signal-Related Kinase

ETT	Endotracheal Tube
FDA	Food and Drug Administration
GDNF	Glial cell derived neurotrophic factor
GFAP	Glial Fibrillary Acidic Protein
GMFCS	Gross Motor Function Classification System
HCT	Hematocrit
HIE	Hypoxic-Ischemic Encephalopathy
HIPAA	Health Insurance Portability and Accountability Act
HT	Hypothermia
HUS	Head Ultrasound
ICE Trial	Infant Cooling Evaluation Trial
IL	Interleukin
IND	Investigational New Drug
IP	Intraperitoneal
IRB	Institutional Review Board
IV	Intravenous
JAK2	Janus Kinase 2
MAR	Missing at Random
miITT	Modified Intent to Treat
MCAR	Missing Completely at Random
MRI	Magnetic Resonance Imaging
MRS	Magnetic Resonance Spectroscopy
MSD	Meso Scale Discovery
NDI	Neurodevelopmental Impairment
NEAT	Neonatal Erythropoietin in Asphyxiated Term Newborns
NEATO	Neonatal Erythropoietin and Therapeutic Hypothermia Outcomes in Newborn Brain Injury
NINDS	National Institute of Neurological Disorders and Stroke
NS	Normal Saline
NSE	Neuron-Specific Enolase
OT	Occupational Therapy

PENUT	Preterm Erythropoietin Neuroprotection Trial
PI	Principal Investigator
PI3K	Phosphatidylinositol-3 kinase
PT	Physical Therapy
QA	Quality Assurance
SAE	Serious Adverse Event
SC	Subcutaneous
SD	Standard Deviation
SOP	Standard Operating Procedure
ST	Speech Therapy
STAT5	Signal Transducer and Activator of Transcription 5
TNF- α	Tumor Necrosis Factor- α
TOLSURF	Trial of Late Surfactant
UCH-L1	Ubiquitin C-terminal Hydrolase-L1
VEGF	Vascular Endothelial Growth Factor
WIDEA	Warner Initial Developmental Evaluation of Adaptive and Functional Skills

## 1. General Design Considerations

### 1.1 Hypothesis

Epo given to infants with moderate-severe HIE will safely lead to improved neurodevelopmental outcome at 24 months.

### 1.2 Design

This study is a randomized parallel group double-masked, placebo-controlled trial in neonates with HIE. We will enroll 500/2 = 250 subjects in each of two treatment groups: Epo-treated vs. placebo control. Eligible neonates will be enrolled and treated with either Epo or normal saline (on study day 1,2,3,4, and 7) and followed for a fixed period of 24 months ( $\pm 56$  days) for survival and neurological outcomes. For extenuating circumstances, for example, COVID-19 restrictions, the in-person elements of the final endpoint evaluation may be performed up to 36 months of age. The follow-up period was chosen to provide meaningful motor and cognitive outcomes, since CP and motor and cognitive deficits are more reliably diagnosed at 2 years of age. Enrolled children will be randomized, stratified by study site and severity of HIE, with equal likelihood to receive Epo or saline.

### 1.3 Randomization

Randomization sequences will be created centrally by the Data Coordinating Center (DCC). The DCC will provide each site pharmacy with a randomization look-up table that pairs each study ID with a treatment allocation. Randomization is stratified by site and HIE severity level (“moderate” vs. “severe” HIE) based on the modified Sarnat score. The site pharmacy will then draw up the assigned study drug dose into a syringe, based on the randomization list. The appearance of the syringes of Epo and placebo are identical, thus the bedside staff remain masked. Only the research pharmacist and DCC biostatistician will be un-masked to treatment assignment. All parents, study and clinical staff, as well as all Clinical Coordinating Center (CCC) members, will remain masked to treatment assignment throughout follow-up. To ensure balance within clinical centers, the randomization will be implemented using a randomly permuted blocks design to ensure approximate balanced assignments within site and HIE severity level. The sequence of assignments for each site and stratum will be prepared in advance by the DCC.

### 1.4 Analysis

Analyses will be based on a modified Intention to Treat (mITT) approach. In this approach, all randomized neonates who received at least one dose of study drug will be included in the analyses. Neonates whose parents withdrew consent after randomization and before the first dose will be excluded from the mITT.

## 2. Primary Outcome

We used standardized, validated neurological and developmental assessments at 24 months:

- CP diagnosed by Standardized Neurological Examination
- Bayley III Cognitive Score
- GMFCS

The **primary outcome is the composite of death or any neurodevelopmental impairment**.

Neurodevelopmental impairment (mild, moderate, or severe) is defined as any of the following:

- GMFCS level  $\geq 1$ , or

- GMFCS = 0 or 0.5 AND CP (any type), or
- Bayley III Cognitive Score < 90

Due to COVID-19 restrictions, the Bayley III, Neuro examination, and GMFCS data collection windows were extended from their original window of 22-26 months of age up to 36 months of age. The Bayley III is normed by age through 36-months, and CP status is not anticipated to change between 22 and 36 months of age. Therefore, this window extension does not affect the validity of the primary outcome measure.

## **2.1 Motor Deficit - Cerebral Palsy (CP)**

Cerebral palsy (CP) will be determined by a Standardized Neurologic Examination conducted under the direction of [name] (Co-I), using the systematized exam and video-based certification system created for the NINDS-funded ELGAN and PENUT studies. This training program provides a formal method of neurologic testing that is highly reproducible. The exam was created specifically to determine the presence and classification of CP (i.e., quadriplegic-QP, hemiplegic-HP and diplegic-DP) at age 2. To standardize the quality of neurologic examination findings, two follow-up examiners at each site will participate in a training session, review training videos, and submit a set of independently scored examinations that will be used for certification, as was done in the PENUT trial. A re-certification process will be performed at least every 18 months to ensure that primary outcome examiners remain adequately trained throughout the study. Inter-observer variability assessments will be done to determine agreement with gold standard responses. Annotated feedback will be given to examiners regarding items that had a < 85% correct rate. Based on experience in the ELGAN study, we expect agreement rates to exceed 90%.

## **2.3 Cognitive Deficit – Bayley III**

Bayley III Cognitive Score < 90 Bayley III Cognitive Score is a standard test used to evaluate early cognitive outcomes in high-risk infants. Severity of cognitive deficit is defined by number of standard deviations (SD) below the mean (i.e., severe, moderate, and mild deficit = -3, -2 and -1 SDs below the mean). Since the Bayley III yields higher cognitive scores than the previous version of the Mental Development Index on the Bayley II, we have defined cut-offs on the Bayley III that are 5-15 points shifted to the right compared to the Bayley II. We consider any Bayley III Cognitive Score < 90 as abnormal, with mild, moderate, and severe ranges as defined in **Table 2**. These definitions are consistent with findings in a contemporary cohort of infants with HIE who underwent hypothermia, and also consistent with cut-offs used in the PENUT trial. Each site will undergo certification by reviewing a “gold standard” Bayley III assessment performed by our research neuropsychologist. Each site psychologist will

then record a Bayley III assessment of a 2-year-old child and submit the test booklet and video recording for review by the research psychologist for feedback. HEAL CCC leadership has experience in performing multicenter Bayley III certification in other NIH funded studies (e.g., PENUT, TOLSURF), and will use the infrastructure in place for these studies. Only Bayley III examiners who have undergone this training and certification will be allowed to perform the 2-year primary endpoint evaluation.

## 2.4 Adjudication of Primary Outcome

There may be cases of only a phone follow-up rather than an in-person visit, or otherwise partial data. The CCC will create an Outcomes Adjudication Committee, who will be masked to the treatment assignment of the child. The Committee will receive all available data on the long-term outcome of these toddlers and will assess whether they can definitively assign a primary outcome level and what it is, or they do not have sufficient information to make that determination and therefore the value will be imputed. This model was successfully previously used in the NO CLD clinical trial long-term outcome.

## 3. Secondary Outcomes

At age 2, we will assess the effect of Epo on secondary outcomes: a) presence of CP, b) severity of motor impairment, c) Bayley III cognitive and language scores, d) epilepsy (i.e.,  $\geq 2$  afebrile, unprovoked seizures), and e) behavioral abnormalities (i.e., attention problems or aggressive behavior) based on the CBCL externalizing score.

Severity of motor impairment will be determined by type of CP and GMFCS level (**Table 1**).

**Table 1. Motor outcome - 4 level classification.**

GMFCS							
	0	0.5	1	2	3	4	5
No CP	None	None	Mild	Moderate	Severe	Severe	Severe
HP or DP	Mild	Mild	Moderate	Moderate	Severe	Severe	Severe
QP	Moderate*	Moderate*	Severe*	Severe	Severe	Severe	Severe

\* It is unlikely that a child with quadriparetic CP will have a GMFCS of 0-1. However, this scenario is possible in cases of bilateral hemiparesis in which arms are more affected than legs. In such cases, the bilateral nature of the deficit, and the significant neurologic abnormalities that are noted on a standardized neurologic examination, warrant a designation of moderate/severe neurodevelopmental impairment.

QP: quadriplegic; HP: hemiplegic; DP: diplegic

Severity of cognitive impairment will be determined by Bayley III Cognitive Score (**Table 2**).

**Table 2. Cognitive outcome – 4 level classification.**

Cognitive Deficit	Bayley II MDI score (Hypothermia trials)	Bayley III Cognitive score (PENUT, HEAL)
Severe (> 3 SD)	$\leq 55$	$\leq 70$
Moderate (2-3 SD)	> 55 and $\leq 70$	70-84
Mild (1-2 SD)	> 70 and $\leq 85$	85-89
None	> 85	$\geq 90$

## 4. Exploratory Outcomes

### 4.1 Ordinal Exploratory Outcome

To elucidate the effect of Epo on all severities of impairment, we will analyze the effect of Epo on the following 4-level outcome: 1) normal, 2) mild motor and/or cognitive impairment, 3) moderate/severe motor and/or cognitive impairment, and 4) death. Use of this measure allows a detailed assessment of potential shifts in the distribution of outcomes toward improved status associated with treatment.

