3 STUDY DESIGN

Overview: We propose a multicenter, randomized, double-masked, placebo-controlled trial to test the hypothesis that Epo given to infants with moderate-severe HIE will safely lead to improved neurodevelopmental outcome at 24 months. We will enroll 500 newborns ≥ 36 weeks gestational age with moderate/severe HIE determined by neurologic symptoms, Apgar score, level of acidosis, and need for resuscitation. Study drug (Epo or placebo) will be given IV on study days 1, 2, 3, 4, and 7.

Primary outcome will be assessed at 24 months. For extenuating circumstances, for example, COVID-19 restrictions, the in-person elements of the final endpoint evaluation may be performed up to 36 months of age. The primary endpoint is the composite of death or neurodevelopmental impairment. Impairment (mild, moderate, or severe) is defined as of any of the following: 1) GMFCS level ≥ 1 , or 2) GMFCS = 0 or 0.5 AND CP (any type), or 3) Bayley III < 90 . Since death is a competing outcome, it is critical to include it in the primary outcome measure.

Secondary analyses at age 24 months: we will assess the effect of Epo on a) presence of CP, b) severity of motor impairment, c) Bayley III cognitive and language scores, d) epilepsy (i.e., ≥ 2 afebrile, unprovoked seizures), and e) behavioral abnormalities (i.e., attention problems or aggressive behavior) based on the Child Behavior Checklist (CBCL) externalizing score.

Additional exploratory analyses include the effect of Epo on sensory deficits that can result from HIE. We will collect 24-month data regarding the presence of cortical visual impairment diagnosed by an ophthalmologist, and hearing impairment requiring hearing aids. To elucidate the effect of Epo on all severities of impairment, we will perform a secondary analysis of the effect of Epo on the following 4-level outcome: 1) normal, 2) mild motor and/or cognitive impairment, 3) moderate/severe motor and/or cognitive impairment, and 4) death. Severity of motor impairment will be determined by type of CP and GMFCS level. Severity of cognitive impairment will be determined by the Bayley III Cognitive Score.

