### **5. Data Analyses**

#### **5.1 Primary Outcome**

The primary analysis will be a test of equality of the rate of the primary outcome (death or neurodevelopmental impairment (NDI)) across the two randomized investigational groups. Specifically, we will use a likelihood ratio test based on logistic regression, with stratification by recruitment center and HIE severity. We will perform modified Intention to Treat (mITT) analysis and expect minimal non-compliance due to the nature of the intervention in relation to in-patient care. For the primary endpoint, we expect uniform and complete ascertainment of death but may not evaluate all subjects for developmental impairment. We plan to perform a primary analysis based on complete cases and will exclude those subjects for whom vital status is known (alive) but NDI cannot be assessed. Sensitivity analysis will use multiple imputation to evaluate the potential impact of any missing data. Secondary analysis will consider an ordered categorical two-year status measure (death/severe or moderate impairment/mild impairment/normal), and analysis will be based on generalized Wilcoxon tests.

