#### **5.3 Exploratory Outcomes**

Generalized linear regression models will be used for exploratory binary and continuous outcomes, adjusted for recruitment site and HIE severity. Regression models for ordered categorical outcomes (proportional odds models) will be used to provide treatment effect estimates adjusted for recruitment site and HIE severity. Quantitative measures include MRI-based injury score using the Washington University Standardized Scoring System. For these endpoints, differences and 95% confidence intervals in median brain MRI injury scores between groups will be assessed using bootstrapped resampling with replacement.

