## 7.2 Sample size for efficacy secondary outcomes

Our key secondary long-term outcome is an ordered categorical 24-month status measure that classifies subjects as: dead; moderate or severe impairment; mild impairment; and normal. Use of this measure allows a detailed assessment of potential shifts in the distribution of outcomes toward improved status associated with treatment. Statistical analysis of this outcome will use a generalization of the Wilcoxon test that controls for recruitment site and HIE severity. Regression models for ordered categorical outcomes can also be used to provide adjusted treatment effect estimates.

To consider power we have used 2013 data from three large sites participating in the phase II trial (UCSF, Wash U, CNMC) to estimate the distribution of outcomes within the control group. We calculate power for the stratified Wilcoxon test assuming a set of alternatives that are consistent with the assumption of a 33% rate of death or impairment (Scenarios 1 and 2, **Table 5**) or a 32% rate (Scenarios 3 and 4, **Table 5**) associated with intervention that was used to power the primary analysis. We assume a small effect on the death rate, and compute power for alternative shifts in the distribution of outcomes. For example, in Scenario 1 we assume no reduction in the death rate, and an 8% reduction in the moderate/severe category (relative risk = 0.55), and an 8% reduction in the rate of mild impairment (relative risk = 0.50) which yields 81% power using a two-sided alpha=0.05 test. Scenario 3 considers a larger reduction in the rate of moderate/severe and a smaller reduction in the mild category and yields 90% power. Scenarios 3 and 4 consider a 32% overall rate of impairment or death and yield 90% or greater power. Therefore, our study is adequately powered to detect modest but clinically important shifts in the outcome distribution.

**Table 5. Power analysis for a four-level outcome measure with n=500 patients randomized and assuming 10% loss to follow-up**

	Neurodevelopmental Impairment			Mortality	Power
	Normal	Mild	Moderate/Severe		
Placebo Arm	51%	17%	18%	14%	--
Epo Arm					
Scenario 1	67%	9%	10%	14%	81%
Scenario 2	67%	11%	10%	12%	86%
Scenario 3	68%	9%	9%	14%	86%
Scenario 4	68%	11%	9%	12%	92%

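### The SAP ranks the four-level 24-month outcome both as exploratory and as the key secondary, and nothing says which rank governs

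*SAP*

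**What the plan says.** The outcome is the worst of motor and cognitive status at 24 months in four levels: normal, mild, moderate/severe, death. The current texts rank it as follows.

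- SAP section 3: "we will assess the effect of Epo on secondary outcomes: a) presence of CP, b) severity of motor impairment", continuing to item e). The four-level outcome is not among the items.
- SAP 4.1, within the exploratory section: "Ordinal Exploratory Outcome".
- SAP 5.1: "Secondary analysis will consider an ordered categorical two-year status measure", and "analysis will be based on generalized Wilcoxon tests".
- SAP 5.3, on exploratory outcomes: "Regression models for ordered categorical outcomes (proportional odds models) will be used", for effect estimates adjusted for site and HIE severity. The Wilcoxon test is not mentioned there.
- SAP 7.2: "Our key secondary long-term outcome is an ordered categorical 24-month status measure". It is tested by a Wilcoxon generalization controlling for site and severity, with Table 5 giving power at two-sided 0.05. Ordinal regression is an optional source of adjusted estimates.
- Protocol 9.3.2 and 9.4.2 use the key-secondary wording of SAP 7.2, and Protocol 9.2.2 discusses the outcome under secondary outcomes.
- Protocol section 3: "we will perform a secondary analysis of the effect of Epo on the following 4-level outcome", but in a paragraph that opens with exploratory analyses. Protocol 1.2 does not list it among the secondary efficacy endpoints.
- Protocol 9.3.1 allows either Wilcoxon tests or ordinal regression.

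**The concern.** One SAP gives one outcome incompatible ranks. Because I found no testing order and no alpha allocation for secondary efficacy outcomes in either document, the rank is the only advance statement of how much a shift result should count.

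This matters when the binary primary and the ordinal result disagree. If the primary misses and the shift is significant, the report can cite SAP 7.2 and call it the powered key secondary. If the primary succeeds and the shift does not, the report can cite SAP 4.1 and call it exploratory. Both citations would be accurate, so the choice could be made with the result in view.

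**Working it through.** **1. The plan's power table.** Inputs are 225 evaluable per arm (SAP 7.1.4), two-sided 0.05 (SAP 7.2), and the Table 5 distributions. Site and severity strata are not modelled, because no stratum rates are given.

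Let p be the placebo and q the Epo proportions, ordered from normal to death. Then θ = Σ pᵢ(Σ_{j<i} qⱼ + qᵢ/2), the null variance is V₀ = (1 − Σ p̄ᵢ³)·N/(12nm), with p̄ the mean of the two arms, and power ≈ Φ(|θ − 0.5|/√V₀ − 1.96).

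Scenario 1, with p = (0.51, 0.17, 0.18, 0.14) and q = (0.67, 0.09, 0.10, 0.14):

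- θ = 0.51×0.335 + 0.17×0.715 + 0.18×0.81 + 0.14×0.93 = 0.5684
- p̄ = (0.59, 0.13, 0.14, 0.14), so Σp̄³ = 0.2131
- V₀ = 0.7869 × 450/(12×225×225) = 0.000583, and √V₀ = 0.02414
- Power ≈ Φ(0.0684/0.02414 − 1.96) = Φ(0.87) = 80.9%. Using the variance under the alternative as well gives 81.0%.

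| Scenario | Table 5 | Recomputed, 225 per arm | Recomputed, 250 per arm |
|---|---|---|---|
| 1 | 81% | 81.0% | 84.9% |
| 2 | 86% | 87.7% | 90.9% |
| 3 | 86% | 86.5% | 89.8% |
| 4 | 92% | 91.8% | 94.2% |

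The table reproduces within 2 points at 225 per arm and does not at 250. The rank does not enter the formula. The text of SAP 7.2 gives 90% for Scenario 3, where the table's 86% is the figure that reproduces. The text also describes a smaller reduction in the mild category for Scenario 3 than for Scenario 1, but both rows show 9%.

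**2. How often the rank would matter.** I simulated 400,000 trials per setting at 225 per arm, with the unstratified Wilcoxon test and an unadjusted two-proportion test of not normal (death or NDI). Primary only is either significant minus ordinal significant.

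| Setting | Ordinal significant | Primary significant | Either | Ordinal only | Primary only |
|---|---|---|---|---|---|
| Null | 5.0% | 5.4% | 6.9% | 1.5% | 6.9 − 5.0 ≈ 1.8% |
| Scenario 1 | 81.0% | 93.4% | 93.4% | 0.02% | 93.4 − 81.0 = 12.4% |
| Scenario 2 | 87.7% | 93.3% | 93.6% | 0.3% | 93.6 − 87.7 = 5.9% |
| Scenario 3 | 86.5% | 95.8% | 95.8% | 0.02% | 95.8 − 86.5 = 9.3% |
| Scenario 4 | 91.8% | 95.8% | 96.0% | 0.2% | 96.0 − 91.8 = 4.2% |

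**3. Whether the choice of method matters.** In 2,000 trials each under the null and Scenarios 1, 3 and 4, the Wilcoxon test and the proportional-odds likelihood ratio test disagreed on significance in at most 0.35%.

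**4. Whether one odds ratio describes the planned effect.** Scenario 1 cumulative odds ratios for the better outcome are:

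- Normal: (0.67/0.33)/(0.51/0.49) = 1.95
- Normal or mild: (0.76/0.24)/(0.68/0.32) = 1.49
- Alive: (0.86/0.14)/(0.86/0.14) = 1.00

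These are not proportional.

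**The case against.** The best defence is that what matters statistically is already fixed: the four levels, the test, the stratification factors and, in SAP 7.2, two-sided 0.05. With no alpha assigned to the outcome under either rank, relabelling changes no error rate. That stands, and it limits the point to interpretation. It does not settle which rank a report should use.

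A reader might infer more than the documents support:

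- That the SAP has two competing main tests. It does not. SAP 5.1 and 7.2 both name the Wilcoxon test, and 5.3 and 7.2 use ordinal regression for estimates. Only Protocol 9.3.1 leaves an open choice, and step 3 shows that it has almost no effect on significance.
- That a power calculation shows the outcome cannot be exploratory. SAP 7.3 and 7.4 also give power for imaging and plasma biomarkers, which SAP section 4 lists as exploratory. The conflict lies in the words key secondary, not in the existence of the table.
- That exploratory status rules out inference. No section says so, and SAP 5.4 and 5.7 speak of inference for exploratory biomarker analyses.
- That key secondary is plainly the intended rank. It fits most of the protocol and the power table, but SAP sections 3 and 4 point the other way and no text decides between them.

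**Conclusion.** The point holds as a contradiction of rank within the current SAP. It should be resolved before unblinding, because the rank is the only advance guide to the weight of a shift result.

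Its size is modest. The primary test and its alpha are unaffected, and power is unchanged. Discordant results of the kind that would invite a choice of label occur in about 1.5% of null trials (ordinal only) and about 4 to 12% of trials under the plan's own scenarios (primary only). These figures assume 225 evaluable per arm, the Table 5 distributions, and no stratification or covariate adjustment. The actual stratified analyses could shift them somewhat. The contradiction itself rests on no numerical assumption.

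**What to change.** Before unblinding:

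1. State one rank for the outcome in SAP 3, 4.1, 5.1, 5.3 and 7.2. Key secondary fits the protocol and the power table. In that case, add it to section 3 and retitle 4.1. SAP 5.2 covers only binary and continuous outcomes, so the ordinal method should be stated there too. If the sponsor intends exploratory, remove the key-secondary wording from 7.2 and the secondary wording from 5.1.
2. Keep the site- and severity-stratified Wilcoxon as the single test and the adjusted proportional-odds ratio as the estimate. Align Protocol 9.3.1 with this.
3. Report the cumulative odds ratios beside the common odds ratio, because the plan's own Scenario 1 is not proportional.
4. Say whether the p-value is confirmatory (tested at two-sided 0.05 only after a significant primary) or descriptive.
5. While editing 7.2, reconcile the text on Scenario 3 with Table 5.

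The cost is wording in the SAP and one sentence in the protocol. Sample size, data collection and the primary analysis do not change.
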